
Columbia University Irving Medical Center
Herbert Irving Comprehensive Cancer Center
AAAS4165_Version Date: 07/07/2021

| | |
|---------------------------|---|
| | 
if event resolves to Grade 1 or better within 12 weeks;
 
 • Resume Cobimetinib with dose reduced by 1 level if event resolves to Grade 1 or better within 28 days • If event does not resolve, permanently discontinue atezolizumab (if applicable) and cobimetinib and contact PI. |
| Diarrhea colitis, Grade 4 | 
 • Permanently discontinue atezolizumab (if applicable) and cobimetinib and contact PI; • Refer patient to GI specialist (confirmation and biopsy); • Discontinue medications that may exacerbate colitis while investigating etiology; • If Received Atezolizumab – 
 • Initiate treatment with 1-2 mg/kg/day oral prednisone or equivalent. Convert to 1-2 mg/kg/day oral prednisone or equivalent upon improvement; • If event does not improve within 48 hrs after starting corticosteroids, consider immunosuppressive agent; • If event resolves to Grade 1 or better, taper corticosteroids over ≥ 1 month. |

Table A1.3. Guidelines for managing dermatologic events in response to *atezolizumab, cobimetinib, and/or hydroxychloroquine*

| Event | Action |
|------------------|---|
| General guidance | 
 • Seek dermatologic evaluation for persistent and/or severe rash or pruritis • Consider biopsy unless contraindicated |
| Grade 1 or 2 | 
 • Continue atezolizumab (if applicable), cobimetinib, and hydroxychloroquine • Initiate supportive care. If event does not improve, consider treatment with higher potency topical steroids. • For Grade 2, consider referral to dermatologist • For acneiform rash: consider initiating treatment with topical corticosteroids and oral antibiotics, as clinically indicated. |

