Columbia University Irving Medical Center
Herbert Irving Comprehensive Cancer Center
AAAS4165_Version Date: 07/07/2021

| | |
|--|--|
| | 
cobimetinib. If event becomes clinically manageable within 28 days, resume cobimetinib with dose reduced 1 level. If not, permanently discontinue cobimetinib.
 
 • Initiate treatment with anti-thyroid drug, such as methimazole or carbimazole, as needed; • Consider referral to endocrinologist; • Resume treatment when symptoms are controlled and thyroid function is improving; • If condition is life-threatening, permanently discontinue atezolizumab (if applicable) and contact PI. |
| Symptomatic adrenal insufficiency, Grade 2-4 | 
 • Withhold atezolizumab (if applicable); • Continue cobimetinib. • Refer patient to endocrinologist; • Perform appropriate imaging; • If Received atezolizumab – 
 • Initiate 1-2 mg/kg/day IV methylprednisolone or equivalent; convert to 1-2 mg/kg/day oral prednisone or equivalent upon improvement; • Resume atezolizumab (if applicable) treatment if event resolves to Grade 1 or better within 12 weeks; 
 • If event does not resolve to Grade 1 or better within 12 weeks, or patient is not stable on replacement therapy, permanently discontinue atezolizumab (if applicable) treatment and contact PI. |
| Hyperglycemia, Grade 1 or 2 | 
 • Continue atezolizumab (if applicable) and cobimetinib; |

Columbia University Irving Medical Center
Herbert Irving Comprehensive Cancer Center
AAAS4165_Version Date: 07/07/2021

| | |
|--|---|
| | 
 • Initiate treatment with insulin, as needed; • Monitor for glucose control. |
| Hyperglycemia, Grade 3 or 4 | 
 • Withhold atezolizumab (if applicable); • Continue cobimetinib. • Initiate treatment with insulin; • Monitor for glucose control; • Resume atezolizumab (if applicable) when symptoms resolve and glucose levels are stable. |
| TSH = thyroid stimulating hormone | |
| ^a Corticosteroids must be tapered over ≥ 1 month to ≤ 10 mg/kg/day oral prednisone or equivalent before atezolizumab may be resumed. | |
| ^b Atezolizumab may be withheld for more than 12 weeks to allow for corticosteroid treatment tapering. Course must be agreed upon by the investigator and PI. | |

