| ^c Resuming atezolizumab may be considered in patients who are deriving benefit and have fully recovered from the immune-related event. Patients can be re-challenged with atezolizumab only after approval from both the investigator and the PI. | |

Table A1.7. Guidelines for managing pancreatic events in response to *atezolizumab, and/or cobimetinib*.

| Event | Action |
|---|--|
| Amylase and/or lipase elevation Grade 1 | 
 • Continue atezolizumab (if applicable) and cobimetinib. • Monitor amylase and lipase prior to dosing. |
| Amylase and/or lipase elevation Grade 2 | 
 • Continue atezolizumab (if applicable) and cobimetinib. • Monitor amylase and lipase weekly. • For prolonged elevation (> 3 weeks), consider 10 mg/day oral prednisone or equivalent. |
| Amylase and/or lipase elevation, Grade 3 or 4 | 
 • Withhold atezolizumab (if applicable). • Continue cobimetinib. |

Columbia University Irving Medical Center
Herbert Irving Comprehensive Cancer Center
AAAS4165_Version Date: 07/07/2021

| | |
|-------------------------------------|---|
| | 
 • Monitor amylase and lipase every other day. • If Received atezolizumab – 
 • If no improvement, consult GI and consider 1-2 mg/kg/day oral prednisone or equivalent. • Resume atezolizumab if event resolves to Grade 1 or better within 12 weeks. ^{a,b} • Permanently discontinue atezolizumab and contact PI if event does not resolve to Grade 1 or better within 12 weeks. ^{a,b,c} • For recurrent events, permanently discontinue cobimetinib, and contact PI. |
| Immune-related pancreatitis Grade 2 | 
 • Withhold atezolizumab (if applicable). • Continue cobimetinib. • Refer patient to GI specialist. • If Received atezolizumab – 
 • Upon improvement, initiate 1-2 mg/kg/day IV methylprednisolone or equivalent. Convert to 1-2 mg/kg/day oral prednisone upon improvement. • Resume atezolizumab if event resolves to Grade 1 or better within 12 weeks. ^{a,b} • Permanently discontinue atezolizumab and contact PI if event does not resolve to Grade 1 or better within 12 weeks. ^{a,b,c} • For recurrent events, permanently discontinue atezolizumab, and contact PI. |
| Immune-related pancreatitis Grade 3 | 
 • Withhold cobimetinib. |

Columbia University Irving Medical Center

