Herbert Irving Comprehensive Cancer Center
AAAS4165_Version Date: 07/07/2021

| | |
|-------------------------------------|---|
| | 
 Follow guidelines for atezolizumab (if applicable) for Grade 2 event. |
| Immune-related pancreatitis Grade 4 | 
 Permanently discontinue atezolizumab (if applicable) and consider permanently discontinuing cobimetinib. Contact PI.^c If cobimetinib is withheld and event resolves to Grade 1 or better within 28 days, resume treatment at current dose. If event does not resolve to Grade 1 or better within 28 days, permanently discontinue treatment. Refer patient to GI specialist. If Received atezolizumab – 
 Upon improvement, initiate 1-2 mg/kg/day IV methylprednisolone or equivalent. Convert to 1-2 mg/kg/day oral prednisone upon improvement. If event does not improve within 48 hrs of initiating corticosteroid treatment, consider adding an immunosuppressive agent. If event resolves to Grade 1 or better, taper corticosteroids over ≥ 1 month. |

^a Corticosteroids must be tapered over ≥ 1 month to ≤ 10 mg/kg/day oral prednisone or equivalent before atezolizumab may be resumed.

^b Atezolizumab may be withheld for more than 12 weeks to allow for corticosteroid treatment tapering. Course must be agreed upon by the investigator and PI.

^c Resuming atezolizumab may be considered in patients who are deriving benefit and have fully recovered from the immune-related event. Patients can be re-challenged with atezolizumab only after approval from both the investigator and the PI.

Table A1.8. Guidelines for managing neurologic disorders in response to *atezolizumab, cobimetinib, and/or hydroxychloroquine*.

| Event | Action |
|--------------------|--|
| Neuropathy Grade 1 | 
 Continue atezolizumab (if applicable) and cobimetinib. Withhold hydroxychloroquine. Investigate etiology. |
| Neuropathy Grade 2 | 
 Withhold atezolizumab (if applicable) and hydroxychloroquine; Continue cobimetinib. Investigate etiology. Initiate treatment according to institutional guidelines. Resume atezolizumab (if applicable) if event resolves to Grade 1 or better within 12 weeks.^{a,b} Permanently discontinue atezolizumab (if applicable) and contact PI if event does not resolve to Grade 1 or better within 12 weeks.^{a,b,c} |

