| Neuropathy Grade 3 | 
 Permanently discontinue atezolizumab (if applicable) and contact PI. Withhold hydroxychloroquine. Continue cobimetinib. Initiate treatment according to institutional guidelines. |
| Neuropathy Grade 4 | 
 Permanently discontinue atezolizumab (if applicable) and contact PI. Withhold cobimetinib and hydroxychloroquine. Initiate treatment according to institutional guidelines. |

Columbia University Irving Medical Center
Herbert Irving Comprehensive Cancer Center
AAAS4165_Version Date: 07/07/2021

| | |
|---|--|
| | 
 • If patient stabilizes within 28 days, consider resuming cobimetinib at current dose and resuming hydroxychloroquine at 1 dose level lower. If not, permanently discontinue treatment with these drugs. |
| Myasthenia gravis or Guillain-Barré syndrome, Grade 4 | 
 • Permanently discontinue atezolizumab (if applicable). • Withhold cobimetinib and hydroxychloroquine. • Refer patient to neurologist. • Initiate treatment according to institutional guidelines. • If Received atezolizumab – 
 • Consider 1-2 mg/kg/day oral or IV prednisone or equivalent. • If patient stabilizes within 28 days, resume cobimetinib at current dose, and resume hydroxychloroquine at 1 dose level lower. If not, permanently discontinue cobimetinib and hydroxychloroquine. |
| Meningoencephalitis, all grades | 
 • Permanently discontinue atezolizumab (if applicable) and contact PI.^a • Withhold cobimetinib and hydroxychloroquine. • Refer patient to neurologist. • If Received atezolizumab – 
 • Initiate 1-2 mg/kg/day IV methylprednisolone or equivalent. Convert to 1-2mg/kg/day oral prednisone or equivalent upon improvement. • If event does not improve within |

| | |
|---|---|
| | 
48 hrs of initiating corticosteroids, consider adding an immunosuppressive agent.
 
 • If patient stabilizes within 28 days, resume cobimetinib at current dose, and resume hydroxychloroquine at 1 dose level lower. If not, permanently discontinue cobimetinib and hydroxychloroquine. |

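### Appendix 1 misdrafts three safety rules: pancreatitis steroids wait for improvement, recurrent Grade 3 or 4 enzyme elevation carries no atezolizumab stop, and the Grade 4 colitis steroid conversion changes nothing

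*Combined protocol and SAP*

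**What the plan says.** Section 8.3 of the combined protocol and SAP makes Appendix 1 the source of the action for each category of adverse event. Sections 8.2.1 and 8.2.4 refer to it as well. The rows at issue are these.

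- *Table A1.7, immune-related pancreatitis, Grade 2 and Grade 4.* For patients who received atezolizumab, both rows say: "Upon improvement, initiate 1-2 mg/kg/day IV methylprednisolone or equivalent. Convert to 1-2 mg/kg/day oral prednisone upon improvement". The Grade 3 row holds cobimetinib and otherwise points back: "Follow guidelines for atezolizumab (if applicable) for Grade 2 event".
- *Table A1.7, amylase and/or lipase elevation, Grade 3 or 4.* Atezolizumab is withheld and cobimetinib continues. Atezolizumab is resumed if the event falls to Grade 1 or better within 12 weeks. Otherwise: "Permanently discontinue atezolizumab and contact PI if event does not resolve to Grade 1 or better within 12 weeks". On recurrence: "For recurrent events, permanently discontinue cobimetinib, and contact PI".
- *Table A1.7, immune-related pancreatitis, Grade 2.* The opening actions are the same as in the enzyme row (atezolizumab withheld, cobimetinib continued), but on recurrence: "For recurrent events, permanently discontinue atezolizumab, and contact PI".
- *Table A1.2, diarrhea or colitis, Grade 4.* "Initiate treatment with 1-2 mg/kg/day oral prednisone or equivalent. Convert to 1-2 mg/kg/day oral prednisone or equivalent upon improvement".

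**The concern.** These are instructions that sites act on, and each goes wrong if followed as written.

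In the pancreatitis rows the condition for starting a steroid is improvement, so the patient who most needs treatment does not qualify for it.

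In the enzyme row a patient on all three drugs who has a second Grade 3 or 4 elevation permanently loses cobimetinib. Atezolizumab, the drug the row had withheld, can be restarted once the enzymes settle.

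In the colitis row a site cannot tell whether an intravenous start was meant for the most severe grade that the table covers.

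**Working it through.** No arithmetic beyond counting applies. The check sets parallel rows of Appendix 1 side by side.

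**1. Rows with a steroid conversion step**

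| Row | Starts with | Converts to | Improvement required before the start? |
|---|---|---|---|
| A1.2 colitis, Grade 4 | oral prednisone | oral prednisone | no |
| A1.6 adrenal insufficiency, Grade 2-4 | IV methylprednisolone | oral prednisone | no |
| A1.7 pancreatitis, Grade 2 | IV methylprednisolone | oral prednisone | **yes** |
| A1.7 pancreatitis, Grade 4 | IV methylprednisolone | oral prednisone | **yes** |
| A1.8 meningoencephalitis | IV methylprednisolone | oral prednisone | no |
| A1.14 myocarditis, Grade 2 | IV methylprednisolone (to be considered) | oral prednisone | no |
| A1.14 myocarditis, Grade 3-4 | IV methylprednisolone (to be considered) | oral prednisone | no |
| A1.15 nephrotoxicity, Grade 3-4 | IV methylprednisolone | oral prednisone | no |

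That is 8 rows: 7 name an IV start and 1 an oral start. Of the 7, 2 make the start conditional on improvement and 5 do not.

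**2. Is the pancreatitis condition a slip?** Three things say so.
- The same condition appears again at the end of the instruction, attached to the conversion, which is where the other rows have it.
- The Grade 4 row later suggests adding an immunosuppressant if there is no improvement within 48 hours of starting the steroid. That step is hard to reconcile with a start that waits for improvement. Read literally, a patient who never improves reaches neither treatment.
- The enzyme row of the same table runs the other way: it considers oral prednisone when there is *no* improvement.

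The Grade 3 row takes its atezolizumab guidance from Grade 2. If that reference covers the steroid line, Grade 3 inherits the fault, and the Grade 2 correction mends it.

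**3. Recurrence rules in Appendix 1 that lead to a permanent stop**

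| Row | Atezolizumab at first event | Cobimetinib at first event | Permanently stopped on recurrence |
|---|---|---|---|
| A1.5 pulmonary, Grade 2 | withheld | withheld | both (handled as Grade 3 or 4) |
| A1.7 amylase/lipase, Grade 3 or 4 | withheld | continued | cobimetinib only |
| A1.7 pancreatitis, Grade 2 | withheld | continued | atezolizumab |
| A1.7 pancreatitis, Grade 3 | as Grade 2 | withheld | atezolizumab |

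Three of the four stop atezolizumab; the enzyme row does not. Its only permanent atezolizumab stop is failure to resolve within 12 weeks, so a recurrence that resolves in time lets the drug resume. Section 8.2.4 would allow that patient to continue, since atezolizumab with hydroxychloroquine is two of the three drugs.

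**4. Colitis.** Drug, route and dose range are identical before and after the conversion. The closest parallel is meningoencephalitis in Table A1.8, which has the same two-sentence form and the same 48-hour step but reads: "Initiate 1-2 mg/kg/day IV methylprednisolone or equivalent. Convert to 1-2mg/kg/day oral prednisone or equivalent upon improvement".

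**5. Reach.** Table 10 and its footnote on the metabolic panel list no amylase or lipase test, so 0 such tests are scheduled. The enzyme row applies only when a test is done for another reason.

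**The case against.** A reader might infer that cobimetinib in the enzyme row is simply the wrong drug name, to be replaced by atezolizumab, because the row continues cobimetinib. The documents do not support that. Table A1.4 (AST/ALT above 3 and up to 5 times ULN, and above 5 and below 10 times ULN) continues cobimetinib, then discontinues it along with atezolizumab if a held event does not resolve. Table A1.9 (immune-related ocular toxicity, Grade 2) continues cobimetinib, then stops all three drugs permanently if the event does not resolve. Section 8.3.1 stops cobimetinib permanently on recurrence of certain events, including Grade 4 liver laboratory abnormalities. Stopping cobimetinib may therefore be intended, and a straight swap could delete a real safety stop. What remains is the missing atezolizumab action.

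A reader might also infer that an oral start for Grade 4 colitis is wrong in itself. It is not shown to be. Table A1.5 starts oral prednisone for pulmonary Grade 2 and for Grade 3 or 4, without a conversion step, and the allowance for an equivalent agent already permits an IV start. By then atezolizumab and cobimetinib have been stopped, the principal investigator contacted and a GI specialist involved. This item is close to clerical.

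Finally, clinicians would probably not wait for improvement before giving a steroid. Section 8.2.1 refers atezolizumab toxicity to standard medical practice, and the enzyme recurrence line requires contact with the principal investigator. These points lower the chance of harm. They do not make the wording right, and no other section resolves any of the three rows.

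**Conclusion.** The point holds as a minor one about safety wording. In order of importance:

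1. Two pancreatitis rows literally delay the steroid until the patient improves.
2. One enzyme row gives no atezolizumab stop on recurrence, unlike the Grade 2 pancreatitis row with the same opening actions.
3. One colitis row converts a regimen to itself.

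Items 1 and 3 are visible within the rows. Item 2 is an inference from parallel rows, and it makes no claim that the cobimetinib stop is mistaken. The nesting of bullets in the tables is not relied on, because it may not have survived extraction from PDF.

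The effect is on patient management alone. Sample size, error rates and planned analyses do not change.

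**What to change.** - **Table A1.7, pancreatitis Grade 2 and Grade 4:** delete the opening two-word condition, so that the steroid starts at once and only the conversion waits for improvement.
- **Table A1.7, amylase/lipase Grade 3 or 4:** add a permanent atezolizumab stop to the recurrence line, as in the Grade 2 pancreatitis row. Keep the cobimetinib stop unless the sponsor confirms it was an error. The sponsor should answer this explicitly: stopping both drugs leaves hydroxychloroquine alone, which section 8.2.4 does not allow without the Principal Investigator's approval.
- **Table A1.2, colitis Grade 4:** use the form in Table A1.6, "Initiate 1-2 mg/kg/day IV methylprednisolone or equivalent; convert to 1-2 mg/kg/day oral prednisone or equivalent upon improvement". If an oral start is intended, delete the conversion sentence instead.

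The cost is wording in four rows, with no change to design, data collection or analysis. The amendment already planned before Phase 2 (sections 1 and 4.1.2) could carry it, but Phase 1 patients are managed under the present text, so an earlier clarification to sites is better.
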